3. INTERIM ANALYSIS AND DATA MONITORING COMMITTEE REVIEW

There is no interim analysis in Part 1, however, there is an ongoing safety data monitoring and dose escalation/selection data review meeting by an OC, which includes the SC and IDMC chairpersons.

3.1. Operations Committee Review

During Part 1 of the study, an OC consisting of members of the academic leadership of the study, including the SC and IDMC chairpersons, and clinical and biostatistics representatives from the sponsor (not directly involved in study monitoring) will review ongoing unblinded safety and efficacy data. The OC will be responsible for:

- Reviewing ongoing safety and efficacy data by unblinded subject treatment assignments approximately every 1 to 3 weeks.
- Determining the cohort sizes and number of cohorts for the up to approximately 300 unique subjects in Part 1.
- Making dose-escalation decisions in Part 1, including but not limited to deciding whether to proceed with optional cohorts and at what dose(s).
- Reviewing the data for Part 1.

The details of the OC function and composition, including the dose-escalation decision guidelines are described in the OC charter.

The OC Charter could be revised; therefore, the Charter should be referenced for the most current information since this SAP may not be updated with specific OC changes.

A separate SAP will not be provided for the operations committee review.

During the beginning of enrollment, the OC will be provided and review investigator reported safety and efficacy events. As CEC adjudicated data is available this will also be provided to the committee for review.

3.1.1. Dose Escalation Decision Guidelines

OC will review data in an ongoing basis and make a dose escalation decision with intention to study at least 25 subjects at the current dose before escalating to the next higher dose. Dose escalation will be based on the totality of both efficacy and safety data coming from the current and previous cohorts.

Suggested Stopping criteria: meeting any of the following criteria in the highest dose studied could prohibit further dose escalation

- The lower bound of 1-sided 90% CI for major bleeding endpoint is greater than 2%, 3% or 4%.

The following thresholds for major bleeding, based on these rates, will be referenced and are suggested as a guideline when making dosing decisions. Bleeding that is high enough that it crosses one of the thresholds may require stopping dose escalation.

[Table 2](#) can also be used as a suggested threshold for escalating the dose based on the composite major VTE endpoint (proximal DVT, non-fatal PE or any death).

Table 2: Suggested Threshold to Stop Dose Escalation Based on Number of Subjects with Major Bleeding Events

Number of Events	Number of Subjects with Major Bleeding Events		
	Reference Rate: 2%	Reference Rate: 3%	Reference Rate: 4%
2	Up to 26 (7.7%)	Up to 17 (11.8%)	Up to 13 (15.4%)
3	Up to 55 (5.5%)	Up to 37 (8.1%)	Up to 28 (10.7%)
4	Up to 87 (4.6%)	Up to 58 (6.9%)	Up to 44 (9.1%)
5	Up to 122 (4.1%)	Up to 81 (6.2%)	Up to 61 (8.2%)
6	Up to 158 (3.8%)	Up to 105 (5.7%)	Up to 79 (7.6%)
7	Up to 195 (3.6%)	Up to 130 (5.4%)	Up to 98 (7.1%)
8	Up to 233 (3.4%)	Up to 156 (5.1%)	Up to 117 (6.8%)
9	Up to 272 (3.3%)	Up to 182 (4.9%)	Up to 137 (6.6%)
10		Up to 208 (4.8%)	Up to 156 (6.4%)
11		Up to 235 (4.7%)	Up to 177 (6.2%)
12		Up to 262 (4.6%)	Up to 197 (6.1%)

*Smallest number of events that result in the lower bound of the one-sided 90% confidence interval exceed thresholds.

- The lower bound of 1-sided 90% CI for the difference in any bleeding event rate between the JNJ-64179375 arm and the apixaban arm is greater than 0.

Table 3: Examples Where the Lower Bound of 1-sided 90% CI for the Between-Treatment Difference is Greater than 0

JNJ-64179375	Apixaban	Lower Bound
8/25 (32%)	1/10 (10%)	1%
5/25 (20%)	1/20 (5%)	2%
9/50 (18%)	3/40 (7.5%)	1%

- The lower bound of 1-sided 90% CI for the difference in the composite of major and clinically relevant nonmajor (CRNM) bleeding event rate between the JNJ-64179375 arm and the apixaban arm is greater than 0.

Continual Reassessment Method (CRM), a model based approach commonly used in oncology dose escalation study to determine Maximum Tolerated Dose (MTD), will also be employed to predict event rates in next higher dose to guide the dose escalation process.

After all subjects are expected to have completed the Day 10-14 visit for Part 1, an unblinded data review is planned and the selection of the dose range and doses for Part 2 will be based on the evaluation of the totality of the data but with a focus on the any bleeding and total VTE endpoints.

The following sections describe details of the analysis and summary of Part 1 data.

4. SUBJECT INFORMATION

The number of subjects in each analysis set will be summarized and listed by treatment group, combined JNJ-64179375 treatment group, and overall. In addition, the distribution of subjects by, country, and site ID will be presented unless otherwise noted.

4.1. Demographics and Baseline Characteristics

Table 4 presents a list of the demographic variables that will be summarized by treatment group, combined JNJ-64179375 treatment group, and overall for the safety analysis set(s).

Table 4: Demographic Variables

Continuous Variables:	Summary Type
Age (years)	Descriptive statistics (N, mean, standard deviation [SD], median and range [minimum and maximum]
Weight (kg)	
Height (cm)	
Body Mass Index (BMI) (kg/m ²)	
Categorical Variables	Frequency distribution with the number and percentage of subjects in each category.
Age (18-<50, 50 - <65, 65 - <75, ≥ 75)	
Sex (male, female, undifferentiated)	
Race ^a (American Indian or Alaska Native, Asian, Black or African American, Native Hawaiian or other Pacific Islander, White, Other, Multiple)	
Ethnicity (Hispanic or Latino, not Hispanic or Latino)	
BMI ([underweight <18.5 kg/m ² , normal 18.5-<25 kg/m ² , overweight 25-<30 kg/m ² , obese ≥30 kg/m ²])	

^aIf multiple race categories are indicated, the Race is recorded as 'Multiple'
The following analyses sets (Table 5) will be summarized by treatment group.

Table 5: Analysis Sets

Categorical Variables	
Efficacy (mITT, Per-protocol)	Frequency distribution with the number and percentage of subjects in each category.
Safety* (Safety, Per-protocol)	
All Randomized	All randomized will only be used to summarize subject disposition

*Bleeding event analysis will be based on both safety and per-protocol analysis sets; Adverse events will be based on safety analysis set only

4.2. Disposition Information

Screened subjects and reason for screen failures will be summarized overall at end of Part 1.

The number of subjects in the following disposition categories will be summarized throughout the study by treatment group and overall:

- Subjects randomized
- Subjects receiving study agent
- Subjects completing the study
- Subjects who discontinued study agent
- Reasons for discontinuation of study agent
- Subjects who terminated study prematurely
- Reasons for termination of study

The above categories will include summaries over the time points:

- Day 1 to Day 10-14;
- > Day 10-14 to Week 18;

Listings of subjects will be provided for the following categories:

- Subjects who discontinued study agent
- Subjects who terminated study prematurely
- Subjects who were unblinded during the study period
- Subjects who were randomized yet did not receive study agent.

4.3. Treatment Compliance

-Study agent compliance will be calculated as follows:

- a) For oral apixaban or matching apixaban placebo

Study agent compliance (%) = (actual number of tablets taken/total number of tablets supposed to be taken) x100.

b) For single IV dose of JNJ-64179375 or saline only IV infusion

Study agent compliance (%) = (actual total volume through the IV (mL) administered / total amount through the IV (mL) supposed to be administered) x100.

Remarks: Based on the protocol, the denominators in a) and b) above are expected to be documented in IWRS.

The reasons for not taking the total dose through the IV (mL) will be summarized. The categories for the reasons are:

- Adverse event,
- IV access issue, and
- Other.

The anatomical location of the IV dose administration (Right arm, Left arm) will also be summarized.

4.4. Extent of Exposure

The number and percentage of subjects who receive study agent will be summarized by treatment group

Descriptive statistics for study agent duration (N, mean, SD, median, and range (minimum, maximum) will be presented by treatment group for the safety analysis set.

Duration of exposure for apixaban will be summarized in the following duration categories <1, 2 - <5, 5- <10, 10- <15, ≥ 15 days by treatment group.

Study agent duration is defined as (date of last oral (apixaban) dose of study agent – date of first dose of study agent) +1.

Total dose days of exposure is defined as the total number of days that study agent was administered to the subject (excluding days of study agent interruption).

The total number of dose administrations received will be summarized in the following count categories 1, 2 - <5, 6- <9, 10- <15, 16- <20, 20- <29, ≥ 29 by treatment group.

Descriptive statistics will be presented for the following parameters:

- Number of administrations

4.5. Protocol Deviations

In general, the following list of major protocol deviations may have the potential to impact subjects' rights, safety or well-being, or the integrity and/or result of the clinical study. Subjects with major protocol deviations will be identified prior to database lock and the subjects with major protocol deviations will be summarized by category.

- Developed withdrawal criteria but not withdrawn
- Entered but did not satisfy criteria
- Received a disallowed concomitant treatment
- Received wrong treatment or incorrect dose
- Others

4.6. Prior and Concomitant Medications

Prior and Concomitant medications will be coded using the World Health Organization Drug Dictionary (WHO-DD). Prior medications are defined as any therapy used before the day of first dose (partial or complete) of study agent. Concomitant medications are defined as any therapy used on or after the same day as the first dose of study agent, including those that started before and continue on after the first dose of study agent.

Summaries of concomitant medications will be presented by ATC term and treatment group. The proportion of subjects who receive each concomitant medication will be summarized as well as the proportion of subjects who receive at least one concomitant medication. In addition, concomitant medications of special interest will be presented. These include tranexamic acid (TXA), antiplatelet therapies, anticoagulant therapies, and nonsteroidal anti-inflammatory drug (NSAIDs). See [Attachment 1](#) for Concomitant medications of special interest WHO categories.

Prior medications will be summarized by treatment group and ATC term.

5. EFFICACY

5.1. Analysis Specifications

5.1.1. Level of Significance

As stated in section 1.3 above, no statistical hypothesis will be tested in Part 1 of the study. However, for the OC review of data on an ongoing basis and for making dose escalation decisions, suggested stopping criterion are based on lower bounds of one-sided 90% confidence intervals. These lower bounds when crossed indicate JNJ-64179375 dose(s) not being favorable with respect to the endpoints considered.

For the unblinded data review planned after all subjects are expected to have completed the Day 10-14 visit for Part 1 one-sided 90% confidence intervals will be used for comparing JNJ-64179375 dose(s) with apixaban.

5.1.2. Data Handling Rules

5.2. Primary Efficacy Endpoint(s)

The primary efficacy endpoint is total VTE.

Note: - The focus of Part 1 will be primarily dose escalation based on safety. Total VTE in Part 1 of the study is used to address the secondary objective of assessing the dose response of JNJ-64179375 for the prevention of total VTE.

5.2.1. Definition

Total VTE is defined as the composite of proximal and/or distal DVT (asymptomatic confirmed by venography assessment of the operated leg or objectively confirmed symptomatic), nonfatal PE, or any death.

→ Total VTE = Proximal DVT (Asymptomatic or Symptomatic) + Distal DVT (Asymptomatic or Symptomatic) + Nonfatal PE + Any death

The primary window for analysis of Total VTE is the up to Day 10-14 visit observation period.

The following maps the locations in eCRF of the investigator reported components needed in the definition of total VTE:

Total VTE Component	eCRF Form name (s)	Comments
Symptomatic DVT (Proximal or Distal)	Suspected Symptomatic Deep Vein Thrombosis	In the opinion of the investigator, does this event meet the protocol definition of Symptomatic Deep Vein Thrombosis? YES
Asymptomatic DVT (Proximal or Distal)	Planned Day 10-14 Venography	Proximal clot or Distal clot
Nonfatal PE	Suspected Symptomatic Pulmonary Embolism & Death	Suspected symptomatic PE & Alive
Death	Death	

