9.2.2. Assessments for PE

For all subjects with symptoms of PE, spiral computed tomography (CT), pulmonary angiography, or perfusion/ventilation lung scintigraphy combined with chest radiography will be performed. A diagnosis of PE will be made only if the subject has symptoms of PE (eg, sudden onset of dyspnea, chest pain, or fainting), and 1 of the following criteria is met:

- Positive spiral CT scan of the chest
- Positive direct pulmonary arteriogram
- High probability ventilation/perfusion lung scan (defined as 1 or more segmental or large [>75% of a segment] subsegmental perfusion defects associated with ventilation mismatch)
- Intermediate probability ventilation/perfusion lung scan and ultrasound or venographic evidence of DVT
- Autopsy confirmation

If a subject is diagnosed with a PE meeting the above definitions, a subsequent venography assessment of the operated leg is not required.

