9.2.3. Assessments for Other Thrombotic Events

Other thrombotic events will include MI, ischemic stroke, and peripheral arterial embolism. In addition, events that appear suggestive of study endpoints (eg, transient ischemic attack [TIA], unstable angina) will be reported by the investigator and reviewed by the CEC to ascertain if a thrombotic event has occurred. The investigator will use his/her medical judgment based upon the definitions below to determine if a thrombotic event has occurred.

Myocardial Infarction

The diagnosis of MI requires the combination of:

- Evidence of myocardial necrosis (either changes in cardiac biomarkers or postmortem pathologic findings); and
- Supporting information derived from the clinical presentation, ECG changes, or myocardial or coronary artery imaging.

Stroke

Stroke is defined as a new, sudden, focal neurologic deficit resulting from a presumed cerebrovascular cause and not due to a readily identifiable cause such as trauma, a tumor, or seizure.

If an event matching this definition lasts less than 24 hours it will be considered a TIA unless imaging confirmation of infarction is obtained. Investigators will further classify the strokes based upon imaging studies.

- Primary ischemic infarction stroke without focal collections of intracranial blood confirmed by imaging. The occurrence of hemorrhagic conversion of a primary ischemic infarction will be recorded.
- Primary hemorrhagic stroke with focal collections of intraparenchymal blood. The diagnosis of primary hemorrhagic stroke can only be made with imaging studies. It may include intraventricular hemorrhage.
- Subarachnoid hemorrhage the diagnosis requires documentation by an imaging study
- Uncertain no imaging or autopsy available

Other events of intracranial bleeding such as subdural hematoma and epidural hematoma will not be considered to be a stroke as they are usually traumatic in nature.

Peripheral Arterial Embolism

A peripheral arterial embolism is defined as an abrupt vascular insufficiency associated with clinical or radiologic evidence of arterial occlusion in the absence of other likely mechanisms (eg, trauma, atherosclerosis, instrumentation). In the presence of atherosclerotic peripheral vascular disease, diagnosis of embolism to the lower extremities should be made with caution and requires angiographic demonstration of abrupt arterial occlusion.

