5.4.1. Definition

The following maps the location in eCRF of other efficacy variables

Other Efficacy Variables	eCRF Form name(s)	Comments
Myocardial Infarction (MI)	Suspected Myocardial Infarction/ Unstable Angina	In the opinion of the investigator, does this event meet the protocol definition of Myocardial Infarction → YES
Ischemic stroke	Suspected Stroke / Transient Ischemic Attack (TIA)	In the opinion of the investigator, does this event meet the protocol definition of Stroke → YES

Peripheral arterial embolism	Suspected Peripheral Artery Embolism	In the opinion of the investigator, does this event meet the protocol definition of Peripheral Artery Embolism? → YES
------------------------------	--------------------------------------	---

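### Two eCRF mappings in the SAP select the wrong investigator-reported events: nonfatal PE on suspicion alone, and ischemic stroke on any stroke

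*SAP*

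**What the plan says.** SAP 5.2.1 defines total VTE, with nonfatal PE as one component, and then gives a table introduced by "The following maps the locations in eCRF of the investigator reported components needed in the definition of total VTE". The table has one column for form names and another for comments. In the comments column, the nonfatal PE row reads "Suspected symptomatic PE & Alive". The major VTE table in SAP 5.3.1 repeats this entry.

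The neighboring rows go further. Symptomatic DVT needs a positive answer to "does this event meet the protocol definition of Symptomatic Deep Vein Thrombosis? YES". In SAP 5.4.1, MI needs "does this event meet the protocol definition of Myocardial Infarction → YES" and peripheral arterial embolism needs "does this event meet the protocol definition of Peripheral Artery Embolism? → YES".

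Protocol 9.2.2 is restrictive on PE: "A diagnosis of PE will be made only if the subject has symptoms of PE" and, in addition, one of five objective criteria is met (spiral CT, pulmonary arteriogram, high-probability lung scan, intermediate-probability scan with evidence of DVT, or autopsy).

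The row labelled ischemic stroke in SAP 5.4.1 is selected by "does this event meet the protocol definition of Stroke → YES". Protocol 9.2.3 defines stroke broadly and has investigators classify it by imaging. One of the listed classes is "Primary hemorrhagic stroke with focal collections of intraparenchymal blood"; subarachnoid hemorrhage and uncertain are others. The exploratory endpoint in protocol 2.1.2 is ischemic stroke only.

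**The concern.** **PE.** Followed literally, the SAP counts a subject as having nonfatal PE once a suspicion has been reported and the subject is alive, even when imaging excluded PE. SAP 3.1 has the Operations Committee review investigator-reported events early in enrollment, with adjudicated data added as they arrive. Under SAP 5.2.3 the adjudicated result takes precedence in the best-available count only where both sources exist. Until then, an excluded PE sits in both the investigator-reported and the best-available counts of total and major VTE. SAP 3.1.1 offers Table 2 as a guide for major VTE, and there a high count points toward considering a higher dose.

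**Stroke.** A hemorrhagic stroke would be tabulated as a thrombotic outcome. In an anticoagulant trial that reverses its meaning, since symptomatic intracranial bleeding is a major bleeding criterion in Attachment 2 of the protocol. The table is exploratory and drives no decision.

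**Working it through.** **1. Reading the rows side by side**

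| Row | SAP section | Form title begins with Suspected | Meets-protocol-definition condition |
|---|---|---|---|
| Symptomatic DVT | 5.2.1, 5.3.1 | yes | yes |
| Nonfatal PE | 5.2.1, 5.3.1 | yes | **no** (only alive) |
| MI | 5.4.1 | yes | yes |
| Ischemic stroke | 5.4.1 | yes | yes, but for stroke of any type |
| Peripheral arterial embolism | 5.4.1 | yes | yes |

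PE is the only one of these forms without a confirmation condition. The stroke row is the only one whose condition is wider than its label.

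**2. One-sample bound for major VTE**

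SAP 5.2.3 specifies an exact one-sided 90% lower bound. For x events in n subjects this is the 0.10 quantile of a Beta(x, n − x + 1) distribution. As a check against the plan's own figures, I looked for the largest n at which the bound stays above the reference rate. All 30 filled cells of SAP Table 2 reproduce. For the 2% reference:

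- 2 events: 2/26 gives 2.06% and 2/27 gives 1.99%, so the limit is 26, as in Table 2.
- 3 events: the limit is 55, as in Table 2.

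Adding one excluded PE:

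| Subjects | True events | Bound without it | Bound with it | Crosses 2%? |
|---|---|---|---|---|
| 25 (intended minimum, SAP 3.1.1) | 0 | 0 | 0.42% | no |
| 25 | 1 | 0.42% | 2.15% | yes |
| 25 | 2 | 2.15% | 4.49% | already above 2%; now crosses 3% and 4% |
| 40 (planned per cohort) | 0 | 0 | 0.26% | no |
| 40 | 1 | 0.26% | 1.34% | no |
| 40 | 2 | 1.34% | 2.79% | yes |

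From 27 to 55 subjects, the false event has to come on top of two true ones to cross 2%.

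**3. Between-treatment bound**

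SAP 5.2.3 also specifies a Miettinen-Nurminen one-sided 90% lower bound for the difference from apixaban, compared with 0. The method reproduces SAP Table 3:

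- 8/25 v 1/10 gives 0.87% (plan: 1%).
- 5/25 v 1/20 gives 2.08% (plan: 2%).
- 9/50 v 3/40 gives 1.31% (plan: 1%).

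With 40 JNJ-64179375 subjects and 30 pooled apixaban subjects (the sizes in SAP 1.4):

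- 2/40 v 0/30 gives −0.37%.
- 3/40 v 0/30 gives +2.07%, so one added event crosses 0.
- 3/40 v 1/30 gives −3.90%, so with one apixaban event it does not.

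At a smaller, earlier size of 25 v 10, even 3 v 0 events gives −2.97%, and nothing crosses.

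**4. Stroke**

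The row feeds no threshold, so there is nothing to compute.

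**The case against.** The strongest reply is that these tables only say where data sit in the eCRF. The endpoint is defined in the text above the table, the comments are shorthand, and protocol 9.2.2 still governs. On this reading the stroke row's label already restricts it to ischemic events. The eCRF form and the Data Presentation Specifications, neither of which is available, may hold the missing conditions.

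The shorthand reading does not fit the tables. Form names have their own column, and the comments carry selection logic. The major VTE row for symptomatic DVT is already labelled proximal, yet its comment still adds a proximal condition; the PE comment adds a condition on being alive. A PE row that states a condition but omits confirmation is an incomplete rule. The unseen documents might lead to correct programs, but they cannot make the SAP text correct.

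The objection to the size of the effect largely stands:

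- The final analysis uses adjudicated events (protocol 9.2 and 11.11.4), and the committee adjudicates suspected stroke as well as PE.
- Adjudicated, investigator-reported and best-available counts are shown side by side.
- The VTE guide is permissive: it suggests escalation may be considered where there is no safety issue, and escalation through the planned doses is already the intent (protocol section 11).
- No stated action follows a between-treatment VTE bound above 0. The 40 v 30 example is also a late one, because it pools apixaban subjects from three cohorts.
- Reporting is double-blind, so excluded suspicions can arise in either arm.

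**Conclusion.** Both mappings are wrong as written. The PE rows conflict with protocol 9.2.2, and the stroke row conflicts with the ischemic-stroke endpoint. They should be corrected.

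The consequence is small and confined to Part 1 summaries of investigator-reported events, plus best-available VTE counts until adjudication. An excluded PE can move major VTE past a Table 2 reference, but only when one or two true events are already present at 25 to 55 subjects. How often this would happen is unknown, because the documents give no rate of excluded PE suspicions. The stroke error touches one exploratory summary. Adjudicated results are unaffected.

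The conclusion assumes that the SAP rows are programmed as they read. The eCRF and the programming specifications could not be checked.

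**What to change.** - **SAP 5.2.1 and 5.3.1, nonfatal PE:** select events that the investigator confirms as meeting the protocol 9.2.2 definition of PE, in a subject who is alive.
- **SAP 5.4.1, ischemic stroke:** select events that meet the stroke definition and are classified as primary ischemic infarction. List hemorrhagic, subarachnoid and uncertain strokes separately.

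The cost is three table cells and the matching programming. No new assessment is needed, since protocol 9.2.2 already sets the PE criteria and 9.2.3 already has investigators classify strokes. If the PE form has no question on meeting the definition, either add one or derive the answer from the imaging fields. Sample size and power do not change.
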